## 1 PROTOCOL SUMMARY

### 1.1 SYNOPSIS

- Title:** A Phased Clinical Trial of a Dietary Supplement Kava: Biomarker Changes and Anxiolytic Effects
- Study Description:** This study will examine the utility of plasma and urinary based biomarkers for the anxiolytic properties of kava, a natural dietary supplement. We will conduct a one week, double blind, randomized placebo controlled trial of kava, dosed at three 75 mg capsules per day, vs placebo, in adults with generalized anxiety disorder. Clinical measures of anxiety, blood, and urine will be obtained. Biomarkers of interest include PRKACA, cortisol, urinary TCE, and NA-5HT. CYP2D6 testing will be conducted at the screening visit to examine, at the end of the study, whether kava metabolism through this enzyme affects the biomarker responses. Participants will be assessed pre- and post-treatment. They will also be followed for 12 weeks after the end of treatment to identify any potential rare adverse events, particularly liver toxicity, that appear in a delayed fashion.
- Objectives:** Primary Objective: To evaluate the effect of a one week flavokavain A/B-free kava trial in GAD patients on biomarker and anxiety scale changes, and the relationships between these measures, in a double-blind RCT.
- Endpoints:** Primary Endpoint: Plasma PRKACA, cortisol, urinary TCE, urinary NA-5HT and cortisol levels  
Secondary Endpoints: Compliance determined by missed doses and increased dihydromyricetin (DHM) levels
- Study Population:** We will screen 30 subjects in order to randomize 26 adults with GAD ages 18-50 for entry into the study, with at least 20 of them completing the study. There are no restrictions on ethnicity, social background, or gender. Subjects will only be accepted into the study if they are free of any history of significant medical illness as determined by history taking, physical examination, and routine laboratory tests. Female subjects of child-bearing potential will be given a pregnancy test.

**Phase:** 2

**Description of Sites/Facilities** The University of Florida Clinical Research Center will be used to enroll participants and conduct research procedures. This facility is designed for clinical research.

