## 4 STUDY DESIGN

### 4.1 OVERALL DESIGN

**Aim:** To validate PRKACA reduction (primary outcome), cortisol, urinary TCE, and NA-5HT reductions (secondary outcomes) as biomarkers for kava-induced anxiolysis in GAD.

**Study design:** We will recruit and screen potential participants until we are able to randomize and enroll 26 individuals with GAD, with the expectation that 20 will complete the study (10 per arm) based on a conservative estimate of a 25% drop-out rate (the drop-out rate for our pilot study was 19%). We will build on our prior work with smokers by evaluating the utility of PRKACA as a biomarker for kava-induced anxiolysis among individuals with GAD. A one week double-blinded randomized, parallel, placebo-controlled trial of kava in GAD patients will be conducted. To minimize the risk of adverse events, particularly liver dysfunction, we will use flavokavain A/B-free kava in this study. Participants will be randomized, stratified by sex, to one of two conditions—placebo dosed three times a day or 75 mg of kava dosed three times a day. All pills will be taken with meals. Potential adverse effects will be evaluated via serum liver biochemistries and assessment of clinical symptoms in all participants at baseline, post treatment (day 7) and every 4 weeks for 12 weeks following discontinuation of treatment. Blood and urine for biomarker assessments will be collected at baseline and post treatment (day 7). CYP2D6 testing will be conducted at the screening visit to examine, at the end of the study, whether kava metabolism through this enzyme affects the biomarker responses.

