#### 4.4 END OF STUDY DEFINITION

The study will come to an end when the data for 13 controls and 13 subjects with GAD has been collected and analyzed.

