## 9 STATISTICAL CONSIDERATIONS

### 9.1 STATISTICAL HYPOTHESES

- Primary Efficacy Endpoint(s):
  - Mean PRKACA reduction will be 30% higher in kava group than placebo group
  - Mean PRKACA and HAM-A score reductions in placebo group will be correlated by at least 0.3
- Secondary Efficacy Endpoint(s):
  - Measurable DHM levels will be detected in 8/10 participants in kava arm

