### 9.2 SAMPLE SIZE DETERMINATION

We will recruit and screen potential participants until we are able to randomize and enroll 26 individuals with GAD, with the expectation that 20 will complete the study (10 per arm) based on a 75% success rate (the retention rate for our pilot study was 81%). Of particular interest is determining the utility of measuring changes in PRKACA as a marker of kava-induced anxiolysis. To provide context, the effect size seen in our pilot work was .794 (Cohen's  $f$ ) for PRKACA reductions on kava from baseline. Based on the proposed design, with 10 subjects per arm, we have 0.80 power to detect an effect size (Cohen's  $f$ ) of 0.73 (82, 83). While this represents a large effect size, it is consistent with what was found in our pilot work.

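### The only criterion for the PRKACA–HAM-A link is a correlation of at least 0.3 in about 10 placebo participants, with no planned analysis, interval or power; read as a cut on the observed r, chance alone meets it 20% of the time

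*Combined protocol and SAP*

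**What the plan says.** The primary objective in the Synopsis (1.1) covers biomarker changes, anxiety-scale changes "and the relationships between these measures, in a double-blind RCT". Section 9.1 then puts two hypotheses under the primary efficacy heading. The first is "Mean PRKACA reduction will be 30% higher in kava group than placebo group". The second is "Mean PRKACA and HAM-A score reductions in placebo group will be correlated by at least 0.3".

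Section 9.2 sets the number randomised at 26 and the number analysed lower, "with the expectation that 20 will complete the study (10 per arm) based on a 75% success rate". Its only power statement is "with 10 subjects per arm, we have 0.80 power to detect an effect size" of 0.73 on the Cohen's f scale. That figure is set against a pilot f of 0.794 for PRKACA reduction on kava.

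Section 9.4.1 specifies condition-by-time mixed models for PRKACA, cortisol, urinary TCE and NA-5HT. HAM-A is not modelled and no correlation appears. Section 9.4.2 only points back to 9.4.1, and exploratory analyses (9.4.9) are marked not applicable.

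Sections 2.1 and 4.1 give the aim as validating PRKACA reduction as a biomarker of anxiolysis induced by kava.

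**The concern.** The trial is meant to show that PRKACA tracks the anxiolytic effect, and the 0.3 figure is the only stated standard for that claim. It comes without a null value, a test, an interval, a significance level or a type of correlation. It rests on one arm, which is half the data, and about 10 people.

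If an observed r of 0.3 or more were taken as support for the link, the standard would be weak: such a value is common by chance at this sample size, and it is compatible with anything from a moderate negative to a strong positive relationship.

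The choice of arm adds a second problem. A correlation among people who received no kava describes how the two measures move together without the treatment. It cannot by itself show that PRKACA marks an effect of kava.

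**Working it through.** **Inputs.** Threshold 0.3, placebo arm (9.1). Completers per arm: 10 (9.2). Randomised per arm: 26/2 = 13, assuming equal allocation (9.2; 4.4 also counts 13 and 13). Alpha and sidedness are not stated, so two-sided 0.05 is assumed where a test is mentioned. Pearson correlation and bivariate normal changes are also assumed.

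**1. The plan's own power figure.** For two groups with N = 20 and f = 0.73, the noncentrality is N·f² = 20 × 0.5329 = 10.66 on (1, 18) df. Power is 0.87 at two-sided 0.05 and 0.79 at alpha 0.025. With no alpha stated, the 0.80 can be neither confirmed nor called wrong, and this point does not depend on it. On either reading it is power for a difference in PRKACA, not for a correlation.

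**2. Chance of r >= 0.3 when the true correlation is 0.** Use t = r·√(n−2)/√(1−r²) on n−2 df.
- n = 10: t = 0.3 × √8/√0.91 = 0.890 on 8 df, upper tail 0.200.
- n = 13: t = 0.3 × √11/√0.91 = 1.043 on 11 df, upper tail 0.160.
- n = 8, if dropout is heavier: upper tail 0.235.

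These are one-directional. If either sign counted, the n = 10 figure would be 0.40.

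**3. Precision of an observed 0.3 at n = 10.** Fisher z: arctanh(0.3) = 0.3095, standard error 1/√7 = 0.378. The limits are tanh(0.3095 ± 1.96 × 0.378), that is tanh(−0.431) = −0.41 and tanh(1.050) = 0.78. A two-sided 5% test against zero would need |r| of at least 0.632.

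**4. All completers, adjusted for arm.** Removing the arm effect costs one degree of freedom, so 20 completers give an effective n of about 19.
- Chance of r >= 0.3 when the true value is 0: t = 0.3 × √17/√0.91 = 1.297 on 17 df, about 0.11.
- 95% CI around 0.3: tanh(0.3095 ± 1.96/√16) = tanh(−0.1805) to tanh(0.7995), or −0.18 to 0.66. The width falls from 1.19 to 0.84.
- Power of a two-sided 5% test against zero, by simulation: about 24% at a true 0.3 and 62% at 0.5. For 80% the true value must be near tanh((1.96 + 0.84)/√16) = tanh(0.70) = 0.60.

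Pooling therefore helps, but the trial remains small for this question. Detecting a true 0.3 with 80% power would take about 85 people: ((1.96 + 0.84)/0.3095)² + 3.

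**The case against.** The strongest reply is that 9.1 states an expectation and not a decision rule. No section says that an observed r of 0.3 declares the link shown, and 4.2 and 9.4.1 describe the work as exploring potential and effect sizes. Sections 2.1 and 4.1 name PRKACA reduction alone as the primary outcome. This stands in part: the pass-mark reading is an inference. It is the natural one, because no test is offered and the neighbouring secondary item (8 of 10 with measurable DHM) is also a raw threshold. If 0.3 is instead a population value, the plan still has no analysis to assess it, and 10 people give about 13% power against zero at two-sided 5%. An exploratory purpose argues for an estimate with an interval rather than a number under a primary heading.

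Placebo may also be a slip for kava. Both arms expect 10 completers, so the 20% and the interval would not change, although the mismatch with the aim would ease.

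Three stronger readings are tempting and should not be drawn.
- A reader might infer that the small sample is why a true 0.3 would fall short about half the time. A cut placed at the true value is missed about half the time at any size: 0.478 at n = 10, 0.486 at 20, 0.493 at 85 and 0.495 at 200.
- A reader might multiply 0.80 by the chance of passing the cut to get a joint success probability. No section requires both hypotheses to be met, and 0.80 is power to detect f = 0.73, not the chance of meeting the 30% criterion.
- A reader might infer that 9.2 claims to power the correlation. It gives a Cohen's f directly after a PRKACA pilot effect. The fault is an omission, not a false claim.

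**Conclusion.** The point holds as a gap in specification plus an unreliable criterion. A listed primary hypothesis has no planned analysis, interval or power. If its 0.3 is applied to the observed correlation, unrelated measures meet it in 20% of trials with 10 completers in the arm (16% with 13), and an observed 0.3 is compatible with about −0.41 to 0.78. The single-arm choice uses half the data and, with placebo named, does not speak to an effect of kava.

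The figures rest on Pearson correlation and bivariate normality, and the 20% on the inferred pass-mark reading. The absence of a correlation analysis in 9.4 and the mismatch between placebo arm and aim rest on neither. The documents do not show that the sponsor would declare a link from 0.3 alone, only that nothing else is provided by which to judge it. This should be corrected.

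**What to change.** - **9.1 and 9.4.1/9.4.2:** replace the placebo-arm threshold with the partial correlation, adjusted for arm, between PRKACA change and HAM-A change over all completers in both arms. Report it with a 95% CI, and show the two per-arm correlations alongside as descriptive. State that no link will be declared from r >= 0.3 alone. Define both changes by visit, since the Schedule of Activities takes HAM-A at the phone screen and Week 1 but the biomarkers at Day 1 and Week 1.
- **9.2:** say that the 0.80 power refers to the PRKACA contrast only. Call the correlation an estimation objective, and note that with about 20 completers a two-sided 5% test against zero would have about 24% power at a true 0.3 and reach about 80% only near 0.6. No such test need be added.

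The cost is wording, with no extra patients, visits or assays. There are two downsides. The pooled estimate assumes the same within-arm relationship on kava and placebo, which the per-arm values can check only roughly. The plan would also state openly that it measures the biomarker-symptom link with low precision.

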### 9.2 SAMPLE SIZE DETERMINATION

We will recruit and screen potential participants until we are able to randomize and enroll 26 individuals with GAD, with the expectation that 20 will complete the study (10 per arm) based on a 75% success rate (the retention rate for our pilot study was 81%). Of particular interest is determining the utility of measuring changes in PRKACA as a marker of kava-induced anxiolysis. To provide context, the effect size seen in our pilot work was .794 (Cohen's  $f$ ) for PRKACA reductions on kava from baseline. Based on the proposed design, with 10 subjects per arm, we have 0.80 power to detect an effect size (Cohen's  $f$ ) of 0.73 (82, 83). While this represents a large effect size, it is consistent with what was found in our pilot work.

### 9.3 POPULATIONS FOR ANALYSES

Individuals with GAD ages 18-50

### 9.4 STATISTICAL ANALYSES

#### 9.4.1 GENERAL APPROACH

In this aim, we will explore the effect of kava supplement on changes in PRKACA, cortisol, urinary TCE, and NA-5HT. Separate 2 x 2 (Condition (Placebo / Kava) x Time (Baseline and Post-treatment, within condition) generalized linear mixed models (GLMM) will be analyzed for (a) PRKACA, (b) cortisol, urinary TCE, and NA-5HT outcomes. Of primary interest is exploring effect sizes for the interaction effect (difference in slopes) for those outcomes over weeks 0 (baseline) to 1 under placebo and kava conditions. Simple main effects will provide information about the within-subjects slope for each condition. GLMM analyses allow for missing data for an intent-to-treat approach, and can accommodate measurement of study subjects at different time points during the study, incorporate time varying covariates, flexible covariance structures, and a variety of dependent variable distributions (including counts and dichotomous) (85, 86). The statistical model will contain main effects for condition and time and the condition by time interaction. Of primary interest is the treatment by time interaction effect, as that will reflect the effect of the kava intervention.

---

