#### 10.1.8 QUALITY ASSURANCE AND QUALITY CONTROL

The site SC will ensure that all study personnel have completed all required institution-specific and protocol-specific trainings and that these trainings are documented appropriately on the Training Log. The site SC will also ensure that new personnel are appropriately documented on the Delegation of Responsibilities Log (DOR). While training should be completed and documented in real time, the Lead SC will verify that all training is current and appropriately documented. All study staff will complete CITI or NIH Human Subjects training prior to commencement of study. The investigators are responsible for ensuring the accuracy, completeness, legibility, and timeliness of the data reported. All source documents should be completed in a neat, legible manner to ensure accurate interpretation of data. The investigators will maintain adequate case histories of study subjects, including accurate case report forms (CRFs), and source documentation. All data will be entered into a REDCap (Research Electronic Data Capture) database developed for this project. REDCap is a secure, HIPAA-compliant web-based application designed to support traditional case report form data capture. Data will be exported into a

SAS data set for analysis. Data integrity will be evaluated using descriptive statistics (e.g., means, standard deviations, frequencies, percent, range) appropriate for measurement levels. Checks for implausible or out-of-range values, distributional forms, and missingness will be performed. Data transformations (e.g., Box-Cox family of transforms) and/or cross product terms will be incorporated, if required, based on evaluation of tenability of statistical model assumptions and model fit to the data. All analyses will be conducted using SAS version 9.4 or later.

---

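### Cheap improvement, not an error: the planned 2 x 2 model fixes the baseline slope at 1; estimating it is more precise up to a pre-post correlation of about 0.87-0.88 if the SDs are equal

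*Combined protocol and SAP*

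**What the plan says.** Section 9.4.1 plans a separate condition-by-time model for each of PRKACA, cortisol, urinary TCE and NA-5HT: "The statistical model will contain main effects for condition and time and the condition by time interaction". The interaction is taken as the kava effect, and the stated purpose is estimation: "Of primary interest is exploring effect sizes for the interaction effect (difference in slopes"). Section 9.4.2 refers back to this text, so it is also the primary analysis. The hypothesis in 9.1 is "Mean PRKACA reduction will be 30% higher in kava group than placebo group".

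There are two measurement times (4.1): "Blood and urine for biomarker assessments will be collected at baseline and post treatment (day 7"). The expected size is given in 9.2: 26 randomised, "with the expectation that 20 will complete the study (10 per arm) based on a 75% success rate". Section 9.4.1 adds that "GLMM analyses allow for missing data for an intent-to-treat approach".

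No section prespecifies adjustment for baseline. Section 9.4.1 notes only that such models can take covariates and flexible covariance structures. Section 10.1.8 leaves additions to model fit: "Data transformations (e.g., Box-Cox family of transforms) and/or cross product terms will be incorporated, if required". On allocation, 4.1 says "Participants will be randomized, stratified by sex, to one of two conditions"; sex appears in no model.

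**The concern.** The condition main effect leaves the two baseline means free to differ, although randomisation makes their expectations equal. The interaction then subtracts each participant's whole baseline value. That is the best weight only when the true regression slope of day 7 on baseline (correlation times day-7 SD over baseline SD) is close to 1. When the slope is well below 1, the change score carries baseline noise into the estimate.

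At stake is the precision of the primary estimate. With about 10 completers per arm and an aim of estimating effect sizes, the width of the interval decides what can be learned, and the baseline values needed to narrow it are already collected.

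**Working it through.** **Inputs.** n = 10 completers per arm, N = 20 (9.2). Two time points (4.1). Model terms from 9.4.1. Not in the documents, so assumed or varied: two-sided alpha 0.05; pre-post correlation rho; k = day-7 SD / baseline SD. A normal model with identity link is assumed throughout.

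**The plan's own power figure.** Section 9.2 gives 0.80 power for Cohen's f = 0.73. Read as a two-group difference, d = 2 x 0.73 = 1.46 and the noncentrality is 1.46 x sqrt(10/2) = 3.265 on 18 df. At two-sided 0.05 this gives 0.87, not 0.80. The comparison below does not depend on that figure. It uses the effect at which the planned contrast has exactly 0.80 power: noncentrality 2.963, or 2.963 x sqrt(2/10) = 1.325 SDs of change.

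**Variances, in units of the baseline variance.**
- Planned interaction (difference in mean change): (2/n)(1 + k² − 2 rho k).
- Estimated slope (ANCOVA; the common-baseline model fitted by REML gave the same estimate to within 1e-6 in complete pairs): (2/n) k²(1 − rho²)(1 + 1/(N − 4)), where the last factor is 17/16.
- Ratio, adjusted over planned: R = (17/16) k²(1 − rho²) / (1 + k² − 2 rho k).

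**Equal SDs (k = 1).** R = (17/16)(1 + rho)/2. Break-even is at rho = 32/17 − 1 = 15/17 = 0.882. Allowing for the t critical values (2.110 on 17 df, 2.101 on 18 df) moves it to 0.867. Simulated interval width gives about 0.87.

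**Power.** Given the baselines, the adjusted noncentrality is 2.963 x sqrt[(1 + k² − 2 rho k)/(k²(1 − rho²))] / sqrt(1 + T²/18), where T has a t distribution on 18 df. Power on 17 df is averaged over T.

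| rho (k = 1) | R | planned power | adjusted power |
|---|---|---|---|
| 0.3 | 0.69 | 0.80 | 0.918 |
| 0.5 | 0.80 | 0.80 | 0.878 |
| 0.7 | 0.90 | 0.80 | 0.836 |
| 0.85 | 0.98 | 0.80 | 0.805 |
| 0.9 | 1.01 | 0.80 | 0.794 |
| 0.95 | 1.04 | 0.80 | 0.784 |

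**Unequal SDs.**
- k = 0.8: R peaks at 0.68 (at rho = 0.8), so adjustment is better at every rho.
- k = 1.1: R is at least 1 for rho about 0.74 to 0.97, and the planned contrast is slightly better there.
- k = 1.2: the same holds for rho about 0.64 to 0.93.

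**Bound on the loss.** 1 + k² − 2 rho k = k²(1 − rho²) + (1 − rho k)². So R never exceeds 17/16, and reaches it only when rho x k = 1. Power there is 0.774, a loss of 0.026.

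**With dropouts.** Take 13 baseline and 10 day-7 values per arm, missing completely at random, with equal SDs. Under the planned model, keeping the baseline-only participants recovers 3/13 (about 23%) of the variance gap. Simulated power (REML with Kenward-Roger, 20,000 trials per setting) is:

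| rho | planned | common baseline |
|---|---|---|
| 0.3 | 0.832 | 0.923 |
| 0.5 | 0.824 | 0.883 |
| 0.7 | 0.817 | 0.842 |
| 0.85 | 0.805 | 0.810 |
| 0.95 | 0.799 | 0.791 |

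With critical values calibrated to 5%, the interval is 13%, 8%, 3% and 0% narrower at rho 0.3, 0.5, 0.7 and 0.85, and 1% wider at 0.9. Type I error was 0.050-0.055 for the common-baseline model and 0.047-0.052 for the planned one. Without a small-sample correction, the common-baseline model's variance is understated (mean 0.142 against an empirical 0.167 at rho 0.5, complete pairs).

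**The case against.** The strongest reply is that this is a choice between two accepted analyses. The planned model is unbiased under randomisation and answers 9.1, and the documents supply neither the correlation nor the SDs needed to show a gain in this trial. If the day-7 SD is 10-20% larger than baseline, the sign reverses at plausible correlations. All of that stands, and it limits the point to an improvement. It does not make the point idle: the possible loss is capped and small, while the possible gain is several times larger.

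The power figures also depend on the chosen effect. At d = 1.46, planned power is 0.87 and adjusted power is 0.93, 0.90 and 0.87 at rho 0.5, 0.7 and 0.85, so the gains are smaller. The variance ratios are unchanged.

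Two further cautions stand. The slope-of-1 statement is exact only for complete pairs in a normal identity-link model, whereas 9.4.1 allows other distributions. And a small part of the simulated power gain may reflect type I error slightly above 5%, although the calibrated interval widths show that most of it is real.

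A reader might infer that the planned analysis is biased, that adjustment always gains power, or that leaving sex out is a fault. The documents support none of these. A constant sex difference cancels from the planned contrast, and nothing shows that sex predicts the change or the day-7 value given baseline.

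**Conclusion.** The point holds as a cheap improvement. Keeping the plan would cost a wider interval, not a wrong conclusion. With 10 completers per arm and equal SDs, estimating the baseline slope cuts the variance by about 31%, 20% and 10% at rho 0.3, 0.5 and 0.7. It makes little difference around 0.85-0.9 and adds about 4% at 0.95. At rho 0.5 the saving is worth about 25% more completers (1/0.80 = 1.25). Over every rho and SD ratio, the completer variance can rise by at most 1/16.

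The size of the gain rests on assumed values of alpha, rho and the SD ratio; the bound does not depend on rho or the SD ratio. The common-baseline model also needs a baseline sample taken before dosing. The synopsis describes pre- and post-treatment assessment, but sections 1.2 and 1.3 put dosing, randomisation and biomarker sampling at Visit 1 without a clear order.

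**What to change.** 1. In 9.4.1, replace the sentence on model terms with wording such as: for each biomarker, the primary model will have an intercept (the baseline mean, common to both conditions), a day-7 indicator, and one treatment term equal to 1 only for kava participants at day 7; an unstructured 2 x 2 covariance; and Kenward-Roger degrees of freedom. The treatment term is the kava effect. These terms are fixed before unblinding and are not subject to the fit-based additions in 10.1.8. Up to sign, the treatment term is still the difference in mean reduction in 9.1, and every randomised participant with a baseline value stays in.
2. Code the treatment term explicitly. Deleting the condition main effect from a categorical time plus condition-by-time model is not enough: that model still has four free means and reproduces the planned analysis.
3. Make the 2 x 2 and simple-main-effects wording in 9.4.1 consistent. Within-condition changes will then use the shared baseline.
4. State that the baseline biomarker sample is taken before the first dose.
5. Add, as a sensitivity analysis in completers, ANCOVA of the day-7 value on condition and baseline. Its t-test is exact under normal errors, which is a useful check on Kenward-Roger here.
6. Optional: adjust for sex, as the stratification factor.

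The cost is a few sentences and a small change to the SAS code, with no new data. The statistical downside in completers is a power loss of at most about 0.026 without sex, or about 0.031 if sex is added to baseline in the ANCOVA.

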### 6.3 MEASURES TO MINIMIZE BIAS: RANDOMIZATION AND BLINDING

Eligible study participants will be randomly assigned to one of two groups: kava supplement or placebo. The pharmacist will use a computerized program SAS PROC PLAN procedure to generate the randomization scheme. Sequentially numbered, sealed, opaque envelopes containing group assignment (kava supplement or placebo) will be prepared by the pharmacist and numbered for each group 1 to 20. When a participant meets criteria to be randomized the study coordinator will open the next (sequentially numbered) appropriate envelope for participant assignment. Because this is a double-blinded study, neither the investigators nor the participants will know whether participants have received the kava supplement or placebo. The placebo supplement will be provided by identical capsules that contain methylcellulose, an inactive ingredient. The pharmacist will distribute identical capsules (kava and placebo); thus, no distinguishing characteristics will be present. The list of prepared supplements will be maintained by the pharmacist who will distribute the appropriate supplements for the next consented, eligible study participant.

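### Randomisation is stratified by sex but the primary model omits sex; if allocation is blocked within sex and sex materially affects biomarker change, the test is conservative and loses power

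*Combined protocol and SAP*

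**What the plan says.** Section 4.1 (Overall Design) says: "Participants will be randomized, stratified by sex, to one of two conditions". Section 9.4.1 (General Approach) gives the model: "The statistical model will contain main effects for condition and time and the condition by time interaction". It names the contrast that matters: "Of primary interest is the treatment by time interaction effect, as that will reflect the effect of the kava intervention". Section 9.4.2 refers the primary endpoint analysis back to that text.

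Sex appears nowhere as a model term. Section 9.4.5 lists gender only as a baseline descriptive, and 9.4.7 plans no subgroup analyses. Section 9.4.1 notes that mixed models can take time-varying covariates, which sex is not. Section 10.1.8 leaves one general opening: "cross product terms will be incorporated, if required, based on evaluation of tenability of statistical model assumptions". That depends on the data and does not name sex.

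On allocation, section 6.3 says: "The pharmacist will use a computerized program SAS PROC PLAN procedure to generate the randomization scheme". It adds sequentially numbered envelopes but gives no block size and does not mention sex. Its remark that envelopes are numbered 1 to 20 for each group could hint at separate lists, but it does not say so.

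**The concern.** Balancing the arms on sex removes sex-related variation from the true treatment contrast. A model without sex leaves that variation in the residual. The computed standard error then describes a less precise trial than the one that was run: intervals are wider than they need be, the actual type I error falls below nominal, and power drops. With about 20 completers there is little precision to spare. The same model form serves PRKACA, cortisol, urinary TCE and NA-5HT, so the omission carries through all four.

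**Working it through.** **Inputs from the plan.** 26 randomised and 20 expected completers, 10 per arm (9.2; 26 × 0.75 = 19.5). Power 0.80 at Cohen's f = 0.73 (9.2). Primary contrast condition-by-time (9.4.1); with two time points and complete pairs this is the between-arm difference in mean change.

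**Assumed.** Two-sided alpha 0.05, because none is stated. Sex effect on change g, in within-sex SDs of change, from 0 to 1.5, because none is given. Half the participants women, except where noted.

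**The plan's own figure.** For two groups d = 2f = 1.46. The noncentrality is 1.46 × √(10/2) = 3.26 on 18 df, giving power 0.870 at two-sided 0.05 and 0.786 at two-sided 0.025. The stated 0.80 is therefore not reproduced at 0.05, where it corresponds to f = 0.66 (d = 1.325). With alpha unstated this does not show 0.80 to be wrong, and it is a separate matter. I use d = 1.325 as the 80% reference.

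**Exact balance within sex (10 women, 10 men, arms equal in each).** Set the within-sex SD of change to 1.

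- True SE of the contrast: √(1/10 + 1/10) = 0.447, whatever g is.
- Expected residual mean square without sex: (18 + 5g²)/18.
- Model SE over true SE: √(1 + 5g²/18). At g = 1: √(23/18) = 1.13.
- Share of variance in change explained by sex: (g²/4)/(1 + g²/4). Shares of 2%, 5%, 10%, 20% and 30% mean g of about 0.29, 0.46, 0.67, 1.0 and 1.31.

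Results at d = 1.325 (2,000,000 draws; 18 df without sex, 17 df with sex-by-time):

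| g | SE ratio, sex omitted | Type I error, sex omitted | Power, sex omitted | Power, sex-by-time included |
|---|---|---|---|---|
| 0 | 1.00 | 0.050 | 0.801 | 0.798 |
| 0.25 | 1.01 | 0.048 | 0.795 | 0.798 |
| 0.5 | 1.03 | 0.044 | 0.780 | 0.798 |
| 1.0 | 1.13 | 0.029 | 0.719 | 0.798 |
| 1.5 | 1.28 | 0.014 | 0.616 | 0.798 |

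**Blocked allocation with dropout.** Here 26 are randomised by permuted allocation within sex and 20 complete at random, so balance is only approximate. The effect is reset for each row to give about 80% power without adjustment (12,000 to 20,000 trials per cell):

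| Variance in change explained by sex | Type I error, sex omitted | Power, omitted → included |
|---|---|---|
| 0% | nominal | 0.794 → 0.783 |
| 2% | not tabulated | 0.797 → 0.794 |
| 5% | not tabulated | 0.799 → 0.807 |
| 10% | about 4.0% | 0.80 → about 0.82 |
| 20% | about 3.5% | 0.80 → about 0.87 |
| 30% | about 2.9% | 0.80 → about 0.90 |

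Including sex-by-time restores type I error to about 5%.

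**Allocation not restricted within sex** (15,000 trials per cell, d = 1.325):

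| g | Model SE / true SE, sex omitted | Type I error, sex omitted | Power, omitted → included |
|---|---|---|---|
| 0 (70% one sex) | 0.460 / 0.461 | 0.052 | 0.783 → 0.754 |
| 0.5 | 0.474 / 0.473 | 0.050 | 0.756 → 0.753 |
| 1.0 | 0.517 / 0.520 | 0.050 | 0.682 → 0.754 |
| 1.5 | 0.581 / 0.584 | 0.053 | 0.581 → 0.750 |

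The unadjusted SE is correct here. What remains is a power gain above about 0.5 SD, against a cost of about 0.03 when sex has no effect.

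**Which term helps.** In one REML mixed-model fit to simulated complete pairs, the interaction SE was 0.305 with no sex term, 0.305 with a sex main effect, and 0.281 with sex-by-time. A main effect shifts both time points equally and cancels out of the change.

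**The case against.** A reader might infer that power is lost whenever sex affects the change. The figures do not support that. Below about 0.2 SD under exact balance, the lost degree of freedom cancels the gain. With dropout, adjusting at a 2% share gave 0.794 against 0.797.

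A reader might also infer that the reported error bars are necessarily too wide. That needs arms actually balanced within sex. Section 4.1 says stratified, but stratified lists without blocks force no balance, and 6.3 mentions no blocks. Nor do the documents supply any sex effect on PRKACA, cortisol, TCE or NA-5HT change. The 10-30% shares correspond to differences of about 0.67 to 1.3 SD, and nothing in the plan makes these more likely than smaller ones.

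Finally, any error is conservative, 9.4.1 frames the aim as exploring effect sizes, and 10.1.8 permits extra cross-product terms.

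These points limit the size and make the standard-error claim conditional. They do not remove the omission. A stratification factor is chosen before any data, so its place in the model should be too, and a clause triggered by model fit does not secure that. Over-wide intervals also matter when the aim is to report effect sizes.

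**Conclusion.** The mismatch between 4.1 and 9.4.1 is real. Its consequence is conditional and moderate. With allocation blocked within sex and 20 completers at an assumed two-sided 0.05, adjusting for sex-by-time changes power by about -0.01 to +0.01 at a 0-5% share, and by about +0.02, +0.07 and +0.10 at 10%, 20% and 30%. Without blocking, the unadjusted analysis is valid and can only be less efficient. In neither case does omitting sex bias the estimate or inflate type I error. The case for the change is that it is cheap and makes the analysis match the design; no large sex effect is known.

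**What to change.** In 9.4.1, replace the model sentence with: *The model will contain condition, time, condition-by-time, sex (the stratification factor) and sex-by-time; the condition-by-time term remains the primary contrast.* Apply it to every biomarker. Do not add sex as a main effect only, since with complete pairs that leaves the primary contrast unchanged.

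In 6.3, state that the allocation lists are prepared separately by sex and blocked within sex.

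The cost is two short text changes and no new data. One residual degree of freedom is lost (18 to 17; critical t 2.101 to 2.110), which under blocked allocation is worth about 0.01 power if sex has no effect. If allocation turns out not to be blocked, that cost is about 0.03, which is why both sections should be changed together.
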